There are many potential sources of bias in study that investigating the efficacy of safety of naloxegol for the prevention of lower GI tract paralysis in critically ill adults and thus a double-blind, placebo-controlled study is the gold standard study design to use. There is no reason to suggest that a dose of greater than 25mg daily of naloxegol (the current FDA-approved dose for the treatment of opioid induced constipation) is not the appropriate dose for this pilot investigation. As outlined in the current package insert, the study dose will be reduced to 12.5mg daily when patients are concomitantly administered a moderate CYP314 inhibitor or who have renal dysfunction (calculated creatinine clearance \leq 60 ml/min). Given that this is a randomized study, the treatment and control groups should be identical. Initiation of docusate 100mg twice daily is a standard of practice in all patients receiving an opioid who are admitted to the medical ICU service at Tufts Medical Center. Given that it remains unknown if naloxegol is efficacious in preventing lower GI tract paralysis in critically ill adults and that half the patients will be administered placebo, all patients will be managed with an aggressive standardized laxative protocol that is based on the most common clinical practices in the ICUs at Tufts Medical Center.

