5.5.2 Doses and treatment regiments

Treatment arm:

Naloxegol 25 mg daily [administered orally (or enterally)]

A lower dose of naloxegol (12.5mg mg daily) will be administered in the following two situations:

- a. A patient who is receiving a moderate CYP3A4 inhibitor that includes diltiazem, erythromycin, fluconazole, or verapamil (at any dose)
- b. A patient with a calculated creatinine clearance (using the modified MDRD approach) ≤ 60 ml/min

This based on the following information included in the Movantik package insert:

Drug Substance: Movantik
 Study Number: ESR-15-11000
 Tufts IRB #12043
 Version: Protocol version #19
 Date: September 10, 2018

- 1 **Under drug interactions: The concomitant use of naloxegol and a moderate CYP3A4 inhibitor may increase naloxegol serum concentrations.** If use cannot be avoided, the dose of naloxegol should be reduced to 12.5mg daily. The investigators are hesitant to exclude all medical ICU patients receiving a moderate CYP3A4 inhibitors from the study given that the list of medications in this list is long and many are used with a high prevalence in the ICU (e.g. diltiazem, erythromycin, fluconazole, or verapamil). With a 12.5 mg naloxegol tablet (and matching placebo) available from AstraZeneca, it will be feasible to administer the lower 12.5 mg daily naloxegol dose to subjects with this potential interaction without compromise the rigor or blinding of the study.
- 2 **Under dosage and administration: The starting dose for patients with a creatinine clearance ≤ 60 ml/min is 12.5 mg daily.** This dose recommendation is based on the fact that some patients with a creatine clearance ≤ 60 ml/min who were exposed to naloxegol 25mg daily were shown to exhibit markedly higher systemic exposure to naloxegol compared to subjects with normal renal function. Given that naloxegol is metabolized through the cytochrome P450 system of the liver, the reason for these high levels is not understood. The investigators are hesitant to exclude all medical ICU patients with a calculated creatinine clearance ≤ 60 mL/min given that this population represents more than 50% of the medical ICU population. With a 12.5 mg naloxegol tablet (and matching placebo) available from AstraZeneca, it will be feasible to administer the lower 12.5 mg daily naloxegol dose to subjects with renal dysfunction without compromise the rigor or blinding of the study.

Note:

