- Renal function often changes (either worsens or improves) during the ICU stay. Therefore, the creatinine clearance will be calculated daily. For a patient whose creatinine clearance drops to ≤ 60 ml/min during the study, the study drug dose will be reduced from 25mg daily to 12.5mg daily. For a patient whose creatinine clearance improves to ≥ 60 ml/min during the study, the study drug dose will be increased to 25 mg daily.
- It is possible that medications with moderate CYP3A4 activity may either be clinical required or stopped during the period of the study. If a patient requires the initiation of a medication with moderate CYP3A4 activity while receiving study medication (and other therapeutic alternatives without this property do not exist), then the study drug dose will be reduced to 12.5 mg daily. If a medication with moderate CYP3A4 activity is stopped during the period of study drug administration then the study drug dose will be increased to 25mg daily on the day after the CYP 3A4 moderate inhibitor is stopped.
- If a patient enrolled in the study requires a strong CYP3A4 medication (and another therapeutic alternative without this property does not exist), then the patient will be removed from the study.

Control arm:

AstraZeneca Naloxegol 25 mg placebo daily [administered orally (or enterally)]

A lower placebo dose of 12.5mg will be used for either of the above situations (ie. #1 or #2) where the 12.5mg daily dose is warranted.

Study drug administration:

If oral study drug medication is not possible (e.g. intubation) then the study drug will be administered via a gastric or enteral tube as recommended in the Movantik package insert. Tube feeds (if being

Drug Substance: Movantik
Study Number: ESR-15-11000
Tufts IRB #12043
Version: Protocol version #19
Date: September 10, 2018

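### A patient who has both reasons for the lower dose and loses only one is ordered 25 mg by the Section 5.5.2 notes while the standing dose rule still requires 12.5 mg

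*Protocol*

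**What the plan says.** Section 5.5.2 of the Protocol sets the standard dose at 25 mg daily and names two circumstances that each call for 12.5 mg:

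- (a) the inhibitor condition: "A patient who is receiving a moderate CYP3A4 inhibitor that includes diltiazem, erythromycin, fluconazole, or verapamil", however small the inhibitor's own dose;
- (b) the renal condition: clearance, estimated by the modified MDRD method, of 60 ml/min or less.

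Two other places confirm that either condition is sufficient. Section 3.2 reduces the dose "when patients are concomitantly administered a moderate CYP314 inhibitor or who have renal dysfunction". The control-arm text in 5.5.2 reads "A lower placebo dose of 12.5mg will be used for either of the above situations".

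The notes in 5.5.2 cover changes during treatment. The first bullet deals with renal function, with clearance recalculated daily. If it falls to 60 or below, the dose goes down to 12.5 mg. If it improves to 60 or above, "the study drug dose will be increased to 25 mg daily". The second bullet deals with moderate inhibitors. If one has to be started, the dose goes down. If one is stopped, "then the study drug dose will be increased to 25mg daily on the day after the CYP 3A4 moderate inhibitor is stopped".

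Section 5.1 refers the reader to Section 5.6 for dose-change requirements. Section 5.6 covers docusate, the laxative guideline and removal from the study, and contains no dose-change rule.

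**The concern.** If either condition alone requires 12.5 mg, then 25 mg is permitted only when both are absent. Each increase instruction in the notes looks at one condition and is silent on the other. For a patient who had both conditions and has lost one, the note and the standing rule give different doses.

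The error runs in the unsafe direction. Followed literally, the notes double the dose in a patient for whom the protocol still calls for the lower one. Section 5.5.2 explains the renal restriction by reporting that some patients with clearance of 60 or less who took 25 mg "were shown to exhibit markedly higher systemic exposure to naloxegol compared to subjects with normal renal function", for reasons it says are not understood. For moderate inhibitors it says that concentrations may rise. Section 1.4(b), which concerns strong inhibitors, names opioid withdrawal as a possible result of supratherapeutic concentrations.

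By the protocol's own account the combination is realistic. Section 5.5.2 puts clearance of 60 or less at more than half of the medical ICU population, describes many moderate inhibitors as commonly used there, and expects both renal function and inhibitor use to change during the stay.

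**Working it through.** No published figure needs reproducing. The check compares the dose under the standing rule with the dose under the notes.

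**Inputs, all from Section 5.5.2**

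- Rule: dose = 12.5 mg if a moderate inhibitor is in use OR clearance ≤60; otherwise 25 mg.
- Note 1: clearance improves to ≥60, so dose = 25 mg. No condition on inhibitor use.
- Note 2: inhibitor stopped, so dose = 25 mg from the next day. No condition on clearance.

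**The four ways to lose one condition, plus the boundary value** (clearances are examples)

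| Before | Change | State after | Rule | Note | Conflict |
|---|---|---|---|---|---|
| Inhibitor only, clearance 80 | inhibitor stops | no inhibitor, 80 | 25 mg | 25 mg | no |
| Clearance 50 only | rises to 75 | no inhibitor, 75 | 25 mg | 25 mg | no |
| Both, clearance 50 | inhibitor stops | no inhibitor, 50 | 12.5 mg, by (b) | 25 mg | yes |
| Both, clearance 50 | rises to 75 | inhibitor, 75 | 12.5 mg, by (a) | 25 mg | yes |
| Clearance 50 only | rises to exactly 60 | no inhibitor, 60 | 12.5 mg, by (b) | 25 mg | yes (equality sign) |

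Of the four substantive transitions, two agree and two conflict. This counts logical cases and is not a frequency. In each conflict the ratio of doses is 25 / 12.5 = 2. The last row is a minor slip: at exactly 60 ml/min both the ≤60 and the ≥60 instruction apply. A related gap is that a patient on two moderate inhibitors who stops one would also be moved to 25 mg under a literal reading of note 2.

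**How many patients**

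The documents give no rate for having both conditions and losing only one. Section 3.1 gives 18 patients on active drug. As an illustration only, with an assumed proportion q of those 18:

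- expected number = 18 × q
- chance of at least one = 1 − (1 − q)^18

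| q (assumed) | Expected patients | Chance of at least one |
|---|---|---|
| 0.02 | 18 × 0.02 = 0.36 | 1 − 0.98^18 = 0.305 |
| 0.05 | 18 × 0.05 = 0.90 | 1 − 0.95^18 = 0.603 |
| 0.10 | 18 × 0.10 = 1.80 | 1 − 0.90^18 = 0.850 |

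These figures carry no more weight than the assumed q.

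**With the joint condition**

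If 25 mg requires clearance >60 AND no moderate inhibitor, rows 3 to 5 all give 12.5 mg under both rule and note, and rows 1 and 2 stay at 25 mg. No conflict remains.

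**The case against.** The best counter-argument is that ordinary reading resolves the point. Conditions (a) and (b) describe the patient's current state and apply every day. Each note bullet follows one condition over time, and the control-arm text after the notes restates the either/or rule. A careful pharmacist would probably keep 12.5 mg, so this would be incomplete drafting of a corner case. It is fair that this is the more natural reading. But the notes are the specific text on dose changes during treatment, they are worded as unconditional orders, and they are what staff would consult on the day an inhibitor stops. Giving the specific instruction precedence over the general rule is also a defensible reading, and no text decides between the two.

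The second argument is that few patients are affected and the harm is limited. Much of this stands:

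- Scheduled erythromycin is excluded at entry (Section 4.2 d), although diltiazem, verapamil and fluconazole are not.
- The second note foresees starting a moderate inhibitor on study only when no suitable alternative exists.
- The disputed dose is the trial's standard dose, given for at most 10 days in an ICU.
- The withdrawal statement in Section 1.4(b) is about strong inhibitors, and Section 1.4(f) calls signs of withdrawal very rare.
- Opioid withdrawal is scored before and 2 hours after each dose, and study drug can be stopped for adverse events.

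These points limit the size of the problem without settling which dose is correct. Withdrawal scoring detects an effect after the dose has been given, and Section 3.1 says it cannot be done during deeper sedation. The daily investigator form (Appendix 10) records clearance but has no field for moderate inhibitors. Bar-scanning checks that the ordered dose is given, not that the order is right.

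Finally, nothing inferential changes. That is correct: sample size, power and the intention-to-treat comparison are untouched.

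**Conclusion.** The concern holds. As written, Section 5.5.2 contains two instructions that give different doses, 25 mg and 12.5 mg, to a patient who had both conditions and has lost one. A minor equality-sign conflict at exactly 60 ml/min sits alongside it. Neither the section nor the cross-referenced Section 5.6 says which instruction prevails.

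The size is a factor of two in dose, in the unsafe direction, for an unknown and probably small number of the 18 patients on active drug. The conflict follows from the text alone and rests on no numerical assumption; only the patient counts depend on the assumed 2% to 10%. This is an internal inconsistency in a dosing rule with a safety consequence, and it should be fixed although it does not affect the analysis.

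**What to change.** Replace both increase instructions in the 5.5.2 notes with one sentence:

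> The dose will be increased to 25 mg daily only when creatinine clearance is above 60 ml/min AND no moderate CYP3A4 inhibitor is in use (from the day after the last one is stopped); both conditions will be checked daily, and the same rule applies to placebo.

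This removes both conflicts, the boundary case at 60 and the case of stopping one of two inhibitors. The cross-reference in Section 5.1 should point to 5.5.2 for dose changes.

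The cost is one amended sentence, one corrected reference and a matching instruction to the investigational pharmacy. No new data are needed: clearance is already calculated daily, and the existing notes already rely on knowing inhibitor use.

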5.5.3 Additional study drug

Under no circumstances will additional study drug (other than that described in 5.5.1) be administered to a subject.

5.5.4 Labeling

Each dose of study medication (whether naloxogol or placebo) will be packaged in a unit of use package by the investigation drug service at Tufts Medical Center and hand delivered to subject's bedside each morning. Each package will be labeled with the following: subject's name, bed number, naloxegol or placebo, strength, the study number and a patient-specific bar code. All normal medication administration screening and documentation procedures for medication administration in the medical ICU at Tufts Medical Center will be used (e.g. bar scanning, computerized medication administration profile etc) to prevent any potential sources for medication-related error.

5.5.5 Storage

All study medication (and placebo) will be stored in Tufts Medical Center Investigational Drug Pharmacy based on the most recent storage recommendations from AstraZeneca. This storage area is in a completely different area of the pharmacy from where normal medication stock is stored. All usual study drug accountability procedures (as outlined in the policies and procedures of the Tufts MC Investigational Drug Pharmacy) will be used for this study. Among the research team, Drs. [name] and [name] will be the primary liasons with members of the Tufts MC Investigational Drug Pharmacy.

5.6 Concomitant and post-study treatment

All patients enrolled in the study will be initiated on the following:

1. Docusate 100mg twice daily administered orally (or enterally).

AND

2. Study Laxative Guideline (see Appendix 1)

Drug Substance: Movantik
Study Number: ESR-15-11000
Tufts IRB #12043
Version: Protocol version #19
Date: September 10, 2018

A standard laxative guideline does not currently exist in any ICUs at Tufts Medical Center. Therefore in an effort to standardize the administration of laxatives in the study, the investigative team developed a study laxative guideline that is similar to current laxative prescribing practices in the medical ICU at Tufts MC for patients that do not have spontaneous bowel movement for ≥ 3 days. Realizing the importance of having a formal, tiered laxative guideline that mimics that which is used in routine practice for medical ICU patients at Tufts Medical Center, the investigators basically formalized the approaches that are most commonly used in practice to develop (what is felt) to be a reasonably aggressive guideline. It should be noted that if study patient fails to have spontaneous bowel movement at 6 days (despite ever more intensive laxative treatment steps occurring), the patient will be removed from the study and the clinical ICU team will have the option of administering SC methylnaltrexone or intervening in whatever way these see fit to treat the constipation. Of course, prior to study day #6, if the medical ICU team feels that a subject's constipation is severe enough to warrant study removal (and perhaps methylnaltrexone administration) then the subject would be removed from the study earlier. It will be communicated to each subject's ICU physician that the study laxative guideline does not have to be rigidly followed if the subject's physician deems that a deviation from the guideline is required based on their clinical evaluation of the subject.

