[Defined as either: i. INR ≥ 2.0 (not related to warfarin therapy) AND total bilirubin ≥ 2 or ii. Diagnosis of liver cirrhosis as defined by Child-Pugh classes B or C or iii. acute liver disease is the primary reason for admission to the ICU.]

- o. Inability to enroll in study and initiate study medication within 72 hours of the patient being first initiated on IV opioid therapy after ICU admission.
- p. Unreliable method for enteral, gastric and/or oral medication administration (e.g., no feeding tube, NG tube is on suction).
- q. Current or previous use of an opioid antagonist agent (e.g., naloxogel, methylnaltrexone) agent in the past 30 days.
- r. Patients expected to expire within 24 hours.
- s. Pregnant or actively lactating females.
- t. Current participation in another interventional clinical study.
- u. Inability to obtain informed consent from either the subject or their legally authorized representative.

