Appendix 1. Study Laxative Guideline

No spontaneous bowel movement in ≥ 3 days⁴?

Step 1: Initiate: Senna one tablet (8.6 mg) PO/NG daily AND polyethylene glycol 3350 17 g PO/NG daily. If SBM occurs then stop step 1 therapy but keep patient on docusate.

No spontaneous bowel movement in ≥ 4 days⁴?

Step 2: Increase Senna to 2 tablets (17.2 mg) PO/NG daily AND polyethylene glycol 3350 to 34 g PO/NG daily and insert a bisacodyl suppository 10mg PR x 1. If bowel movement occurs then stop all laxative study protocol therapy but keep patient on docusate.

No spontaneous bowel movement in ≥ 5 days⁴?

Step 3: Repeat Step 2 AND if no spontaneous bowel movement within 2 hours of administering the bisacodyl suppository, administer a 10oz bottle of magnesium citrate sodium phosphate. If bowel movement occurs then stop all study laxative protocol but keep patient on docusate.

No spontaneous bowel movement in ≥ 6 days⁴?

Step 4: Discontinue study medication (but do not unblind patient assignment). Repeat Step 3, initiate methylnaltrexone (Relistor) sc x once and consider a consultation to gastroenterology or surgery. [Note: If patient weight is 38-62 kg then methylnaltrexone dose = 8mg; if patient weight is 62-144 kg then methylnaltrexone dose = 12mg].

[figure not shown]
⁴From the day of initiation of scheduled opioid therapy (ie. IV fentanyl ≥ 100 mcg/day or equivalent)

Drug Substance: Movantik
 Study Number: ESR-15-11000
 Tufts IRB #12043
 Version: Protocol version #19
 Date: September 10, 2018

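### Section 5.6 and Appendix 1 contradict each other on when and how a non-responder leaves treatment, and the SAP does not say how that patient is then followed

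*Protocol*

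**What the plan says.** **When.** Appendix 1 (Study Laxative Guideline) sets Step 4 at "No spontaneous bowel movement in ≥ 6 days". Its footnote counts every step from the day scheduled opioid therapy begins. Section 5.6 applies "if study patient fails to have spontaneous bowel movement at 6 days" and names no origin. Its next sentence lets the ICU team act "prior to study day #6, if the medical ICU team feels" the constipation is severe enough. Table 1 places randomization on study day 1. Exclusion criterion (o) in 4.2 allows a gap between the two origins, since it excludes only "Inability to enroll in study and initiate study medication within 72 hours of the patient being first initiated on IV opioid therapy". The note in 2.2 likewise allows up to three days.

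**What happens.** Under 5.6, "the patient will be removed from the study and the clinical ICU team will have the option" of giving methylnaltrexone. Appendix 1 Step 4 says "Discontinue study medication (but do not unblind patient assignment" and then "initiate methylnaltrexone (Relistor) sc x once and consider a consultation to gastroenterology or surgery". Section 5.8.1, item 2, stops study drug when Level 4 of the guideline is needed. Section 5.9 keeps collecting outcomes after drug stop, naming only duration of ICU stay as an example, and discards all data if consent is withdrawn.

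**Analysis.** Section 12.2 of the protocol and SAP defines the primary event as three or more days without a SBM after randomization. It treats death or withdrawal before that event as censoring. Section 12.1 states the intention-to-treat principle. Neither document says how a patient removed under 5.6 or stopped at Step 4 enters any SBM analysis.

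**The concern.** Staff cannot follow both texts. A patient without a SBM reaches the removal point at different times on the two clocks, and is then either off study drug but followed, or out of the study.

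These patients are selected by failure to respond. If leaving the study ends their SBM record, the loss is informative, and with 18 patients per group a few such losses matter. The outcomes exposed are time to first SBM and days without a SBM. Treatment duration would also depend on which passage the bedside team applied.

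**Working it through.** **Inputs.** Steps 1 to 4 at 3, 4, 5 and 6 days from opioid start (Appendix 1). Lag L from opioid start to randomization, 0 to 72 h (2.2, 4.2(o), Table 1). Earliest primary event 72 h after randomization (12.2). Study day 6 starts at (6 − 1) × 24 = 120 h if study days are 24 h blocks from randomization (Table 1; the block length is my assumption).

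**Step 4 on the opioid clock.** Time after randomization = 144 h − L.

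| Lag L | Step 4 after randomization | Minus earliest primary event (72 h) | Minus start of study day 6 (120 h) |
|---|---|---|---|
| 0 h | 144 h | +72 h | +24 h |
| 24 h | 120 h | +48 h | 0 h |
| 48 h | 96 h | +24 h | −24 h |
| 72 h | 72 h | 0 h | −48 h |

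The clock origins can be 72 h apart, but the removal points differ by 48 h earlier to 24 h later.

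**Can Step 4 precede the primary event?** In elapsed hours, 144 − L is at least 144 − 72 = 72 h, so it cannot; at L = 72 h they tie. On calendar days it can. Take opioid start at 23:00 on day 0, L = 72 h, and Step 4 at the start of day 6: Step 4 falls 144 − (23 + 72) = 49 h after randomization, 23 h before the event is countable. The footnote counts from a day, not an hour, and the daily forms in Appendices 9 and 10 run from 07:00, so the counting method needs stating. Discretionary removal in 5.6 has no lower time limit and can precede 72 h on any count.

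**Days without a SBM.** The Poisson offset is days in the ICU, capped at 10. As an illustration, suppose a patient has six charted days, all without a SBM, leaves the study, and stays in the ICU for 10 days. If charting stops at removal but the offset does not, the rate is 6/10 = 0.6 instead of 6/6 = 1.0 on the observed days.

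**Time to first SBM.** I first reproduced the plan's power. With constant hazards from 90% vs 40% without a SBM at day 4, HR = ln 0.4 / ln 0.9 = 8.70. Expected SBMs over 10 days = 18(1 − 0.9^2.5) + 18(1 − 0.4^2.5) = 20.3. Power = Φ(√20.3 × ln 8.70 / 2 − 1.96) = 99.8%, the figure in 12.2.2. The 10-day horizon is inferred; the documents do not state it. For 80% vs 50% the formula gives 76.7% (stated: 76.0%).

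If every patient still without a SBM leaves at a single time between 3 and 6 days after randomization, the same formula gives 93.5% to 99.1% for 90% vs 40%, and 43.6% to 64.1% for 80% vs 50%. This is indicative only, because hazards would change after methylnaltrexone.

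**Action, side by side.** Appendix 1 and 5.8.1 stop the drug, 5.6 removes the patient from the study, and 5.9 continues follow-up after drug stop. Methylnaltrexone is an option in 5.6 and an instruction in Step 4. No passage reconciles these.

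**The case against.** The best defence is that there is only one ladder. Section 5.6 refers to Appendix 1, its six days follow a description of the escalating steps, and 5.8.1 keys drug stop to the guideline's fourth level. The study-day phrase occurs once, in a sentence about discretion. Section 5.6 also says the guideline need not be followed rigidly, so a Step 4 instruction and clinician choice can coexist. And intention-to-treat is stated.

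Much of this stands. The opioid clock is the likelier intent for the six-day rule, and the methylnaltrexone difference is the weakest part of the conflict. But the study-day phrase treats day 6 as the removal point, and nothing withdraws it. The intention-to-treat sentence fixes the groups compared; it does not say that SBM data are collected after removal.

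A reader might infer something stronger: that Step 4 removal censors patients just as the primary event becomes countable. The documents do not support that. In elapsed time anyone at Step 4 already has at least 72 h without a SBM since randomization. At the exact tie the usual Kaplan-Meier convention, which the SAP does not state, counts the event before the censoring. The tied patient is also doubtful as a participant: 4.2(o) requires the first dose within the same 72 h, and note 2 in 2.1 excludes pre-existing paralysis, although 4.2 does not list it.

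**Conclusion.** The contradiction is real and lies in the wording. Staff are given two possible clocks for the six-day point, separated by −48 to +24 h depending on lag, and two dispositions: drug stop with follow-up, or removal from the study. The −48 to +24 h range rests on elapsed hours, a lag of 0 to 72 h, and study day 6 starting at 120 h.

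The primary endpoint is largely protected. Step 4 patients are already events, so a rule declaring them events would change almost nothing. Two routes can still remove a patient first: discretionary early removal, and calendar-day counting (up to about 23 h before). The main exposure is treatment duration, follow-up after Step 4, time to first SBM and days without a SBM. Its size depends on how many patients reach Step 4, which the documents do not give.

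Laxative Steps 1 to 3 can also start before the primary event is countable when the lag is long. That follows from the opioid clock alone and is a separate question from this conflict.

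**What to change.** **Protocol.** Reconcile 5.6, 5.8.1 (item 2), 5.9 and Appendix 1 on three things: the clock origin (opioid start or randomization), elapsed hours or calendar days, and stopping study drug or removal from the study. Align the wording on methylnaltrexone between 5.6 and Step 4. Which clinical rule applies is for the investigators; none is proposed here.

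**SAP.** Add wording such as: *SBM data continue to be collected after study drug is stopped, or after removal under the laxative guideline or at the ICU team's discretion, to the end of the outcome window, unless consent is withdrawn. These patients, including those removed before 72 h, are not censored as withdrawals in the primary analysis. Days counted in the Poisson offset match the days on which SBMs were recorded.* State also how a SBM after methylnaltrexone is counted.

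**Cost.** Edits in four places in the protocol and a short SAP paragraph. Table 1 lists SBM documentation as routine ICU nursing care, so continued charting in the ICU should add little work.
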